1.5 PRELIMINARY DATA

Over 10% of patients develop an AKI consistent with CIN after contrast-enhanced CT imaging. These patients are also at significantly increased risk of severe outcomes over the following year. In the largest cohort published to date, the PI and her collaborator ([name]), prospectively followed 633 unselected patients undergoing contrast-enhanced CT imaging for the outcomes of AKI consistent with CIN and 1-year major adverse outcomes including death, renal failure and cardiovascular events (stroke, myocardial infarction, other vascular events requiring

medical or surgical intervention). Notably, this is a larger cohort than that planned for the proposed study. The incidence of CIN was over 10% in all patients,²⁰ and 15% in the population undergoing CTPA.⁷ There was no difference in the rate of CIN among inpatients compared to patients discharged after imaging. After adjusting for age and comorbidities, the development of CIN was associated with a markedly increased risk of death (Figure 2)^{7,11,20} and an increased risk of major adverse events, including renal failure and arterial vascular events requiring intervention, at 1-year (adjusted RR 2.36 95%CI 1.5 to 3.7). The risk of severe outcomes increased with severity of AKI.^{11,20}

The study investigators have previously developed methods of identifying patients evaluated for PE that can be safely randomized: A co-investigator for this study ([name]) derived and validated an attribute matching method to individually quantify the pre-test probability of venous thromboembolism (VTE, PE or deep venous thrombosis [DVT]), PE PreTest Consult Score (PreTest Consult©; v2.1Q; CP Diagnostics, LLC; Charlotte, NC).^{47,56-59} (Figure 3) The PE PreTest Consult Score leverages prospective data from over 8,000 patients evaluated for PE, by CTPA or VQ, at 7 medical centers (6 in the United States and 1 in New Zealand) and is openly available

(<http://pretestconsult.com/v21/pe>). Importantly, this method of assessing pre-test risk of VTE is *well-accepted and used by physicians at medical centers throughout the United States.*¹²

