We acknowledge that the primary outcome of CIN is likely to occur in patients that remain asymptomatic, as expected for the first stages of AKI. We do plan to measure and report patient-center, symptomatic, severe outcomes (see *Secondary Endpoints*) occurring within 1-year. Aside from our own preliminary data,^{7,11,20} there are no consistent, published, prospective data, with sufficient long-term follow-up,^{32,45} in the emergency care setting, or other comparable heterogeneous, ambulatory population (pre-exposure renal function ranging from normal to impaired). Moreover, there are no prospective, controlled data, in any setting, that can be used to adequately design (and determine the sample size for) a study primarily aimed at measuring the long-term, severe outcomes subsequent to CIN. Hence, we have focused on the first phase of AKI, CIN, as the primary outcome, and plan to use the data to inform future research quantifying the effect of selected contrast media exposure on the prevention of long-term severe outcomes subsequent to the development of CIN.

To determine sample size, we conservatively estimated an overall AKI rate of <20%. The sample size was determined based on a Chi-square test (two-tailed, 5% type I error). A sample size of 188 in the CTPA group (exposed) and 269 in the VQ group (unexposed) in each group will have 80% power to detect an absolute difference of 10%. Assuming up to 5% screening and randomization failures (patients assigned to VQ, but undergo CTPA imaging) and a 30% dropout rate,^{7,11,20,53,89} we will recruit 300 subjects per group. (nQuery 2014; Statistical Solutions©)

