Data Analyses Plan: We will select patients with low and moderate risk of PE and a normal chest radiograph. This selection strategy is designed to minimize "crossover" (randomized to VQ/no exposure, but go on to need a CTPA/exposure) (ACR Appropriateness Criteria® <https://www.guideline.gov/popups/printView.aspx?id=35135>, accessed 4/27/2016). Based published literature and our preliminary data, we conservatively anticipate that the crossover rate will be <5% using this selection strategy (see *Preliminary Data and Tables 3 and 4*).⁴⁹⁻⁵² Patients both the CTPA (exposure) and VQ (no exposure) groups will have the same post-test probabilities of PE and the risk of AKI (primary outcome) is not affected by the presence or absence of PE. For all analyses, patients will be considered in the groups to which they are randomly assigned. Statistical significance will be defined by the two-sided p-value <5% (SAS® v 9.1; SAS Institute Inc.).

Baseline Data Analyses: For each of two groups, we will be summarize continuous variables by group using descriptive statistics and categorical variables by frequency counts and percentages. Baseline clinical and demographic data will be compared between two groups to assess the effectiveness of the randomization. Dichotomous and ordinal variables will be examined using chi-square tests and continuous measures with Student's t-tests. Exploratory analysis will be performed to compute p-values which will be presented as an aid to evaluate the overall comparability of the two groups at baseline.

Missing Data Analysis: We anticipate a possible screening and randomization failures (5%)⁴⁹⁻⁵² and dropout (30%)^{7,11,20,53,89} and have adjusted the sample size. It is very unlikely that the dropout mechanism will depend on the unobserved outcome and we will compare the baseline covariates between the dropout and non-dropout groups for substantial differences. Under circumstances where compromise of power may be compromised by missing values, we will use a multiple imputation procedure to make use of all relevant observed data and assume that the data are Missing At Random (MAR), using the SAS® MI and MIANALYZE procedures.

Primary Outcome Analysis: For our primary aim, we will test the following hypothesis:

$$H_0 : |\varepsilon| \geq \delta \quad \text{vs.} \quad H_a : |\varepsilon| < \delta; \text{ where } \varepsilon = P_1 - P_2 \text{ and } \delta = 10\%$$

P_1 and P_2 are the true AKI rates in the CTPA and VQ groups, respectively.

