5.1 Main Measurements

Collection of blood and urine samples may be obtained around enrollment and the initial follow-up (2-7-days). We will collect blood and urine samples, using standard collection methods.

Enrollment Data Collection: The study coordinator will collect the following data: age; sex; race and ethnicity; vital signs; current medications and treatments (including anticoagulation and/or thrombolysis treatment for VTE); comorbid conditions (acute and chronic); the type and severity of prior adverse reactions to iodinated contrast media; physiologic indicators of acute disease (EKG findings of cor pulmonale, indications of right-heart strain and other echocardiography data, cardiac biomarkers including troponin and brain natriuretic peptide [BNP], and lactate); and literature-derived risk factors for CIN.^{18,23,28,41,60-83} We will also record the type and volume of intravenous fluid administered 12 hours prior to and within 24 hours following the enrollment imaging study.

Baseline Creatinine Measurement If the study participant received a baseline creatinine measurement, documented in the EMR, within 24 hours of imaging around enrollment, this measurement will be used as the baseline measurement for our study. If not, we will measure a creatinine level from the blood sample collected at enrollment, if applicable.

Follow-up Creatinine Measurement The follow-up blood draw and creatinine measurement will be performed no sooner than 48 hours and no longer than 7 days (168 hours) following the enrollment imaging study using methodology established by the applicant.^{7,11,20,89} At the time of enrollment, regardless of plans for discharge or

hospitalization, study participants will be scheduled for a return visit to their site of enrollment. The patient will receive a reminder card with the date, time, and location of their follow-up appointment and a contact phone number for the study coordinator. If the patient remains hospitalized 48 hours or more following the enrollment imaging study, we will record the highest creatinine value measured during the specified follow-up time of 2-7 days, or if needed, complete the creatinine measurement. If the patient is hospitalized, but discharged prior to the follow-up period, follow-up will be completed as previously scheduled. A \$50 dollar stipend will be provided for patients that complete the return appointment as reimbursement for travel costs and time.

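### With 30% of outcomes expected to be missing, no analysis shows whether the 10-point equivalence conclusion survives dropout that is not missing at random

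*Combined protocol and SAP*

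**What the plan says.** Section 2.1 (Missing Data Analysis) anticipates 30% dropout and states: "It is very unlikely that the dropout mechanism will depend on the unobserved outcome". The check offered is that "we will compare the baseline covariates between the dropout and non-dropout groups for substantial differences"; whether this is done by arm is not said. Multiple imputation with the SAS MI and MIANALYZE procedures, assuming MAR, is planned where missing values may compromise power.

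Section 2.1 (Primary Outcome Analysis) declares the arms equivalent if two one-sided 5% tests on the raw arm proportions both reject a 10-point difference. That test is not linked to the imputation. Covariate adjustment appears only in the logistic model for the later superiority step.

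Section 5.1 sets two routes to the outcome. For inpatients, "If the patient remains hospitalized 48 hours or more following the enrollment imaging study, we will record the highest creatinine value" within the 2-7 day window, or a measurement is arranged if needed. Patients discharged before the window must return.

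No delta-adjusted, tipping-point, best/worst-case or other not-at-random analysis appears anywhere in the document.

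**The concern.** The plan makes an assumption about 30% of its primary outcomes and offers a check that cannot test it. Baseline covariates can show that dropouts differ in measured ways. They cannot show whether, among patients alike at baseline, those who did not return had more or less AKI. The complete-case test needs missingness that does not distort the arm comparison, and the imputation needs MAR. Neither shows what happens if its assumption is wrong.

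This matters more in an equivalence trial, where bias that shrinks the observed difference favours the claim. Patients know whether they had CT or scintigraphy, so return could differ by arm in ways linked to kidney outcome. If AKI among the missing is worse in CTPA relative to VQ than it is among completers, a true difference at or beyond the margin can pass as equivalence, and nothing planned would reveal it.

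**Working it through.** **Inputs.** From section 2.1: 300 recruited per group, 30% dropout, 5% screening and randomization failures, margin 10 points, one-sided 5% tests (z = 1.645). From section 4.4: 1:1 allocation. The documents give no per-arm event rates and no AKI rates in dropouts; those below are assumptions, shown as ranges.

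**1. The plan's own figure.** The sample size is "based on a Chi-square test (two-tailed, 5% type I error"), and "will have 80% power to detect an absolute difference of 10" percentage points, with "we conservatively estimated an overall AKI rate of <20" per cent. Assuming 20% v 10%:

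n = [1.96√(2 × 0.15 × 0.85) + 0.842√(0.20 × 0.80 + 0.10 × 0.90)]² / 0.10² = 199 per arm

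199 / (0.70 × 0.95) = 299.2, i.e. 300. The recruitment target is reproduced. The stated evaluable pair of 188 and 269 is less clear (188 is what 19% v 9% requires, and 188 / 0.70 = 269), but nothing here rests on it.

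**2. How much is missing.** 0.30 × 300 = 90 missing and 210 completers per arm. Extreme imputation can move the arm difference by 90/300 = 30 points, three times the margin.

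**3. Tipping point.** Let D be the completers' difference (CTPA minus VQ) and d the difference among the missing. The overall difference is 0.7D + 0.3d. Equivalence is lost on the upper side when

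0.7D + 0.3d + 1.645 × SE = 0.10, with SE = √[p1(1−p1)/210 + p2(1−p2)/210].

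- Completers 15% v 15%: SE = 0.0348, 1.645 × SE = 0.0573, d = (0.10 − 0.0573)/0.3 = **14.2 points**.
- Completers 20% v 20%: SE = 0.0390, 1.645 × SE = 0.0642, d = (0.10 − 0.0642)/0.3 = **11.9 points**.
- Completers 18% v 15%: SE = 0.0362, 1.645 × SE = 0.0595, d = (0.10 − 0.0595 − 0.021)/0.3 = **6.5 points**. This is 3.5 points more than the completers' own 3-point gap. The complete-case upper limit is already 3 + 5.95 = 8.95 points.

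The SE is that of 210 completers per arm. If imputed values are treated as observed, the 15% v 15% case tips when CTPA dropouts reach about 32% rather than 29%, with VQ dropouts at 15%.

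**4. False equivalence at the margin.** The true difference is 10 points, so equivalence should be declared about 5% of the time. Each probability is the sum of the binomial probabilities of all outcomes (210 v 210) that pass the plan's two tests.

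*(a) CTPA dropout ignorable, VQ completers at 9%, missing VQ patients with less AKI.* True VQ rate = 0.7 × 9% + 0.3 × (missing rate); true CTPA rate is 10 points higher and equals the CTPA completers' rate.

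| Missing VQ rate | True VQ | CTPA | Completers' difference | P(equivalence) |
|---|---|---|---|---|
| 9% | 9.0% | 19.0% | 10.0 | 5% |
| 4.5% (half) | 7.65% | 17.65% | 8.65 | **11%** |
| 0% | 6.3% | 16.3% | 7.3 | **22%** |

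*(b) True rates 20% v 10%, VQ dropout ignorable, AKI in CTPA dropouts q times that in CTPA completers.* CTPA completers' rate = 0.20/(0.7 + 0.3q).

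| q | CTPA completers | CTPA dropouts | Completers' difference | P(equivalence) |
|---|---|---|---|---|
| 1 | 20.0% | 20.0% | 10.0 | 5% |
| 1.5 | 17.4% | 26.1% | 7.4 | **20%** |
| 2 | 15.4% | 30.8% | 5.4 | **42%** |

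**The case against.** The plan's assumption is not baseless. Section 2.1 says CIN is likely to occur in patients who stay asymptomatic, which weakens any direct link between AKI and returning. Section 5.1 gives every participant a scheduled visit, a reminder card and a stipend, and adds telephone, email and record follow-up for those who miss it. The events schedule (section 5.3) also lists primary-outcome assessment at the 7-day follow-up. All this makes outcome-dependent loss less likely. It does not exclude it: an interview supplies no creatinine, and section 1.4 itself says routine surveillance after exposure is not common practice, so a missed visit will usually leave no value in the record.

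The inpatient and return-visit routes in section 5.1 might be read as proof that dropout depends on the outcome. They are not. The routes apply to both arms, disposition is observed, and imputation that includes arm and disposition can handle loss driven by admission. Only what remains after that is at issue.

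The tipping points can also look remote. At 15% v 15%, with CTPA dropouts at the completers' rate, missing VQ patients would need AKI of about 15 − 14.2 = 0.8%. That is fair; the conclusion is fragile mainly when completers already differ by a few points. It is a reason to report the tipping point, since its plausibility depends on data not yet seen.

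**Conclusion.** The concern stands in a limited form: the equivalence result has no pre-specified sensitivity analysis for data missing not at random, and the assertion that stands in for one cannot be checked by the planned comparison. It should be corrected. The size depends on assumed rates: tipping gaps of about 6.5 to 14 points, and false equivalence of 11% to 22% under mechanism (a) or 20% to 42% under mechanism (b), against 5%. The direction of any real bias is unknown.

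Five stronger readings are not supported:

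- *That the comparison of randomised groups is a failed missing-data check.* The plan's stated purpose is different: "Baseline clinical and demographic data will be compared between two groups to assess the effectiveness of the randomization".
- *That the dropout check certainly pools the arms.* That is the natural reading, but the text is silent. A by-arm version could expose different covariate-related loss in each arm, yet still could not test dependence on the outcome.
- *That the plan defends its assumption with the preliminary finding in section 1.5, "There was no difference in the rate of CIN among inpatients compared to patients discharged after imaging".* It never cites that finding for dropout.
- *That VQ patients will return mainly when ill.* No section reports return by arm.
- *That such behaviour alone would push false equivalence to 40%.* With VQ completers at 9%, that figure needs a 20-point gap among the missing, so completers differ by (10 − 0.3 × 20)/0.7 = 5.7 points and CTPA completers are at 14.7%. If CTPA dropouts resemble CTPA completers, the gap cannot exceed 14.7 points even with no AKI in any missing VQ patient. Rates near 40% require CTPA dropouts to be much sicker than CTPA completers, as in (b).

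**What to change.** In section 2.1 (Missing Data Analysis):

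1. Delete the statement that outcome-dependent dropout is very unlikely.
2. Report by arm the share of patients with a primary outcome, and the baseline characteristics and disposition (admitted or discharged) of completers.
3. Pre-specify a sensitivity analysis of the equivalence test with the MI and MIANALYZE procedures already named. Put arm and disposition in the imputation model, and shift the AKI odds of missing patients separately in CTPA and VQ over a stated range.
4. Report the shift at which the 10-point conclusion changes, and call equivalence robust only if that shift is judged implausible.

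The third and fourth items are essential; the second is supporting description. The cost is a few lines of text and extra SAS runs, with no new data beyond what is already collected. The downside is that the equivalence claim may have to be worded more cautiously.

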Patients will be enrolled in the emergency departments of five hospitals: 1. IUH Methodist Hospital (which also provides emergency care services at IUH University Hospital), 2. Eskenazi Health (formerly Wishard) Hospital, IUH Ball Memorial Hospital, University of Utah, and Intermountain Healthcare. Patients may also complete their imaging studies and, for patients hospitalized >48 hours, may complete their initial follow-up at IUH University Hospital. Examination of data for all emergency department patients who have had a CTPA scan ordered from the two enrollment sites over the past three years reveals mean age 49 ± 16 years with 54% African American, 44% Caucasian, 0.8% Asian, 1% American Indian 1% report Hispanic Ethnicity, and 51% are females; payers include Medicare (22%), Medicaid (25%), Private or commercial insurance (19%) and self-pay (34%). The patients have a high burden of comorbidities, and approximately 65% of all patients are admitted to the hospital. These demographic data match up well with those published in the last three National Hospital Ambulatory Medical Care Surveys (NHAMCS)—a survey designed to collect data on the utilization and provision of ambulatory care services in hospital emergency and outpatient departments. Findings are based on a national sample of visits to the emergency departments and outpatient departments of non-institutional general and short-stay hospitals.⁹⁸⁻¹⁰⁰ Additionally, the table below shows the demographic characteristics of a large sample of patients evaluated for possible PE in 12 emergency departments, not including any hospitals in Indianapolis.¹⁰¹ The almost 2:1 predominance of women undergoing CTPA scanning from the emergency department setting has been shown repeatedly in the United States, and to a lesser extent, in Europe.^{55,102}

Demographics of Patients Evaluated for Pulmonary Embolism in the Emergency Care Setting

12 Centers Not Including Indianapolis

Indianapolis

	n = 7940		n = 200
	n	% or Mean	% or Mean
Age		49±16	49±16
Female	5328	67%	65%
White	4541	57%	61%
Black	2704	34%	29%
Hispanic	482	6%	9%
Asian	74	1%	1%
Other Race	139	2%	<1%

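### Multiple imputation of the primary outcome depends on an undefined loss of power rather than on risk of bias, so the handling of an expected 30% missing outcomes is left open

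*Combined protocol and SAP*

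**What the plan says.** All references are to the combined protocol and SAP.

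- **Trigger (section 2.1, Missing Data Analysis).** The only stated condition for imputing is "Under circumstances where compromise of power may be compromised by missing values, we will use a multiple imputation procedure". When used, the imputation assumes data missing at random. How much loss of power counts, on which test, and when this is judged are not stated.
- **Assumed mechanism (same paragraph).** "It is very unlikely that the dropout mechanism will depend on the unobserved outcome". Baseline covariates of dropouts and non-dropouts will be compared, but nothing follows from the result.
- **Sample size (section 2.1).** The basis is a two-sided chi-square test at the 5% level with 80% power for a 10-point difference. The numbers are worded as "A sample size of 188 in the CTPA group (exposed) and 269 in the VQ group (unexposed) in each group". The allowance for losses is "Assuming up to 5% screening and randomization failures (patients assigned to VQ, but undergo CTPA imaging) and a 30% dropout rate", and the plan arrives at 300 per group. The only AKI rate given is an overall one, put below 20%; no arm-specific rates appear. The Missing Data paragraph confirms that N already allows for the expected dropout.
- **Primary test (section 2.1, Primary Outcome Analysis).** Two one-sided z-tests against a 10-point margin, written in the estimated rates and n1, n2. Patients are analysed as randomised, but how a patient without a follow-up creatinine is counted is not stated.
- **Outcome capture (section 5.1, Follow-up Creatinine Measurement).** Patients still in hospital at 48 hours or later have a value taken from their stay or measured there. All others must come back to the site, including those admitted but discharged before the window opens.

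**The concern.** With 30% of primary outcomes expected to be missing, the main risk is bias in the risk difference. A rule that responds only to loss of power does not address that risk. Because N was inflated for exactly this loss, power may look adequate while the estimate is distorted.

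The rule is also not operational. Two statisticians could apply it to the same data and disagree on whether to impute, and the choice could be made after outcomes are seen.

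The stakes are higher because the first primary test is for equivalence. Loss that hides part of a true difference pushes the result towards equivalence, one of the conclusions that section 1.2 says would change imaging practice. The two capture routes make outcome availability depend on clinical course after randomisation, so missing outcomes need not resemble observed ones.

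**Working it through.** **Inputs from section 2.1:** two-sided 5% chi-square test, 80% power, 10-point difference, 188 and 269, 30% dropout, 300 per group, 10-point equivalence margin with one-sided 5% tests. **Assumed:** the arm-specific AKI rates, because the plan gives only an upper bound of 20%.

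**1. Reproduce the plan's sample size.** The usual formula is n = [1.96√(2p̄q̄) + 0.842√(p1q1 + p2q2)]² / (p1 − p2)².
- At 19% vs 9%: (1.96√0.2408 + 0.842√0.2358)² / 0.01 = 187.8, so 188 per arm. At 20% vs 10% it gives 199.
- 188 / 0.70 = 268.6, so 269. Then 269 / 0.95 = 283.2, so 284, which the plan takes up to 300.

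The figures therefore fit 188 evaluable per arm and 269 after dropout, although the text attaches them to CTPA and VQ.

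**2. Is the trigger met on that basis?** At 30% loss, 300 × 0.70 = 210 remain per arm. Power = Φ{[0.10 − 1.96√(2p̄q̄/n)] / √[(p1q1 + p2q2)/n]}.
- 20% vs 10%: (0.10 − 0.0683) / 0.0345 = 0.919, power 82%.
- 19% vs 9%: (0.10 − 0.0664) / 0.0335 = 1.004, power 84%.

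Both exceed 80%. Power falls below 80% only at about 34% and 38% missing respectively. On this basis the trigger is not met, and the test formula would be filled with observed cases.

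**3. Is it met on the equivalence test?** With zero true difference and common rate p, SE = √(2pq/210) and power = 2Φ(0.10/SE − 1.645) − 1.

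| Common AKI rate (assumed) | SE | Power at 210 per arm |
|---|---|---|
| 10% | 0.0293 | 92% |
| 12.5% | 0.0323 | 85% |
| 15% | 0.0348 | 78% |
| 20% | 0.0390 | 64% |

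At 15% or more the trigger could be met. It would also be met if 269 were read as the evaluable number needed in the VQ arm, since 210 < 269. The same data can thus lead to either choice.

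**4. What could be at stake (illustration only).** Let 30% drop out in each arm, let D be the true difference, and let g be the excess of the arm difference among dropouts over that among completers. Then D = 0.7Dc + 0.3(Dc + g), so the completer difference is Dc = D − 0.3g. Take D = 10 points, which lies on the margin, VQ at 10% and 210 per arm. The false-equivalence rates below come from exact enumeration of the plan's two one-sided tests.

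| Assumed g | Completer difference | False equivalence |
|---|---|---|
| 0 | 10 | 5.2% |
| 10 | 7 | 23.4% |
| 20 (extreme) | 4 | 59.9% |
| −10 | 13 | 0.7% |

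Normal-approximation check for g = 10: SE = √[(0.17×0.83 + 0.10×0.90)/210] = 0.0332, and Φ(0.03/0.0332 − 1.645) = Φ(−0.74) = 23%. With VQ at 5% or 15%, the g = 10 result is 31.2% or 19.9%.

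If VQ stays at 10% throughout, g = 10 means AKI of 27% in CTPA dropouts against 17% in CTPA completers (0.7×17 + 0.3×27 = 20). For g = 20 the rates are 34% against 14%. Nothing in the documents supplies or suggests these gaps.

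**The case against.** **The plan has some support for its assumption.** Section 1.5 reports no difference in CIN between inpatients and discharged patients in the 633-patient cohort. Section 2.1 expects AKI mostly in patients without symptoms, which weakens the idea that return depends on how a patient feels. Both points stand, but every patient in that cohort had contrast. It cannot show that the difference between exposed and unexposed arms is the same in patients with and without an outcome.

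**Missing data are not ignored.** The plan inflates N, compares dropouts with non-dropouts, names imputation procedures, and uses reminders, a stipend and inpatient capture. This reduces the problem but does not settle the primary analysis, and imputation under missing at random cannot repair loss that depends on the outcome.

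**The bias needs an arm-specific gap.** If admission or symptoms affect return equally in both arms, no such gap need arise, and an opposite gap makes false equivalence less likely. This stands; the false-equivalence figures show sensitivity and are not a forecast.

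**Two stronger readings are tempting.** A reader might infer that the plan defaults to complete cases. It never says so, and step 3 shows that the trigger could be met on the primary test. A reader might also infer, from the statement that "approximately 65% of all patients are admitted to the hospital", that nearly all analysed patients would be inpatients. Section 5.1 does not support that, because admitted patients discharged before the window must also return. The 65% describes emergency department patients with a CTPA order at two sites, not the randomised AKIrisk ≥2 group at five.

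**Conclusion.** The concern holds as a defect of prespecification. Imputation of the primary outcome hangs on an undefined loss of power, no action follows from the dropout comparison, and no analysis covers data not missing at random, although 30% loss is expected. At 210 per arm the trigger is not met on the chi-square basis (82% to 84%). It could be met on the equivalence test (78% at a common rate of 15%, 64% at 20%). These powers rest on assumed AKI rates. The rise in false equivalence from 5% to 23% rests further on equal 30% dropout in both arms, VQ at 10% and an assumed 10-point gap; the 60% case is extreme. The documents establish neither that such a bias will occur nor that it will not. This should be corrected before outcome data are examined.

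**What to change.** In section 2.1, Missing Data Analysis:

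1. Remove the power condition. State that the primary equivalence test uses multiple imputation in all cases, carried out separately by arm.
2. Name the imputation variables from data already planned: site, PE PreTest stratum, AKIrisk items, baseline creatinine and admission status. Add NGAL and Cystatin-C where available; sampling is optional in the text, so these may themselves be incomplete.
3. Report the observed-case analysis as a sensitivity analysis.
4. Add a delta-adjusted tipping-point analysis that varies the AKI rate imputed for dropouts by arm and reports the gap at which the equivalence conclusion fails. This is needed because imputation under missing at random does not address outcome-dependent loss.

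The cost is SAP wording and modest extra analysis work. No new data and no change in sample size are required.
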